Urine Drug Screening	X	X				
Alcohol Breathalyzer	X	X				
Pregnancy ⁴	X	X				X
FSH ⁵	X					
Plasma PK ⁶			X	X	X	
Dose Subjects ⁷			X	X		
Concomitant Medication ⁸	X	X	X	X	X	X
Adverse Event Assessment ⁸		X	X	X	X	X

Notes to the Schedule of Events for Part B:

BMI = Body Mass Index; C-SSRS = Columbia-Suicide Severity Rating Scale; ECG = Electrocardiogram; FSH = Follicle-Stimulating Hormone; HbA1c = Hemoglobin A1c; HBsAg = Hepatitis B Surface Antigen; HCV = Hepatitis C Virus; HIV = Human Immunodeficiency Virus; PK = Pharmacokinetic

¹ Only Weight will be recorded at Follow-up, height and BMI will not.

² Vital Signs will be measured at Screening, Check-in, Day 1 prior to the first dose and at 0.5, 1, 1.5, 2, 4, 6, 8, and 12 (±30 min) hours post first dose, prior to the first dose and 2 hours (±30 min) post first dose on Days 2-7, 24 and 48 hours (±30 min) post Day 7 dose, and at Follow-up.

³ ECG will be measured in triplicate at Screening, Check-in, Day 1 prior to the first dose and 1, 2, 3, 4, 5, 6, and 8 hours (±30 min) post first dose, prior to first dose on Days 2-7, and Day 8 (24 hours (±30 min) post Day 7 dose).

⁴ Serum pregnancy test at screening and Urine pregnancy test at Day 0 and Day 15 for all females of childbearing potential.

⁵ FSH test for postmenopausal women.

⁶ Plasma PK samples will be collected on Day 1 prior to the first dose and 15, 30, and 45 minutes (±5 minutes), and 1, 1.5, 2, 3, 4, 6, 8, 12 and 16 hours (±15 min) post first dose, Days 2-6: prior to first dose, Day 7 prior to the first dose and 15, 30, and 45 minutes (±5 minutes), and 1, 1.5, 2, 3, 4, 6, 8, 12, 16, 24, 32, and 48 hours (±15 min) post first dose.

⁷Subjects are required to fast for approximately 12 hours prior to the first Day 1 dose. On Days 1-6, subjects will receive 2 doses per day (8 AM and 8 PM \pm 1 hour) separated by approximately 12 hours. On Day 7, subjects will receive 1 dose (8 AM \pm 1 hour).

⁸ Concomitant Medication and Adverse Event Assessment will be recorded once per day on the days indicated.

TABLE OF CONTENTS

1.	SY	NOPSIS	5
2.	LIS	ST OF ABBREVIATIONS AND DEFINITIONS OF TERMS	20
3.	IN'	TRODUCTION	22
	3.1	Background and Rationale	22
	3.2	Description	23
	3.3	Nonclinical Pharmacology	24
	3.3	3.1 Pharmacodynamics	24
	3.4	Clinical Experience and Pharmacokinetics	24
4.	OF	BJECTIVES	26
5.	ST	UDY DESIGN	27
	5.1	Overall Study Design and Plan	27
	5.2	Discussion of Study Design	29
	5.3	Study Sites	29
	5.4	Selection of Study Population	29

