In Part B, eligible subjects, in 3 cohorts, will be randomized on Day 1 (pre-dose) to placebo (n=2) or LB-102 (n=6) treatment for a total of 24 subjects. Four (4) visits will be scheduled for this study: Screening (Visit 1, Days -28 to -1), Check-in (Visit 2, Day 0), Treatment Evaluation (Visit 3, Days 1-9), and Follow-up (Visit 4, Day 15). The study procedures for these visits are presented in

detail in Table 2. Dosage of LB-102 will be based on the PK observed in a minimum of two Part A cohorts. Subjects will receive 2 doses of placebo or LB-102, first dose at 8:00 AM (±1 hour) and second dose approximately 12 hours later, on Days 1-6 and one dose at 8 AM (±1 hour) on Day 7 for a total of 13 oral doses. The first dose on Day 1 will occur following a 12 hour, overnight fast. For each cohort, blood samples for PK will be collected at multiple timepoints starting on Day 1 at pre-dose and at 15, 30, and 45 minutes (±5 min), and 1, 1.5, 2, 3, 4, 6, 8, 12, and 16 hours (±15 min) post first dose. On Days 2-6, blood samples for PK will be collected prior to the first dose. On Day 7 blood samples for PK will be collected pre-dose and at 15, 30, and 45 minutes $(\pm 5 \text{ min})$, and 1, 1.5, 2, 3, 4, 6, 8, 12, 16, 24, 32, and 48 hours $(\pm 15 \text{ min})$ post first dose. Vital signs will be recorded for each subject at Screening, Check-in, Day 1 at pre-dose and at 0.5, 1, 1.5, 2, 4, 6, 8 and 12 hours (±30 min) post first dose on Day 1, at pre-dose and 2 hours (±30 min) post first dose on Days 2-7, 24 and 48 hours (±30 min) post Day 7 dose, and at Follow-up. 12-lead ECG will be done in triplicate at Screening, Check-in, Day 1 at pre-dose and 1, 2, 3, 4, 5, 6, and 8 hours (±30 min) post first dose, prior to first dose on Days 2-7, and on Day 8 (24 hours (±30 min) post-dose Day 7). Clinical labs will be assessed at Screening, Check-in, prior to first dose on Day 4, Day 8, and at Follow-up. HbA1c will be measured in serum at Screening. Prolactin will be measured in serum at Screening, Day 4, Day 9, and Day 15. C-SSRS will be assessed at Screening, Day 4, and Day 8. Subjects will remain in the clinic from Check-in to Discharge on Day 9 for additional safety assessment and then return for a Follow-up Visit on Day 15. Subsequent groups will follow the same study procedures.

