When there are two or more procedure (ECG, Vital Signs, and PK) scheduled for the same timepoint, the procedures will be as close to the time point as possible and in the following order: ECG, Vital Signs, and then PK blood collection.

The PK profile will include AUC_{0-t}, AUC₀₋₂₄, AUC_{0-inf}, AUC_{wextrap}, CL/F, C_{max}, T_{max}, λ_z, and t_{1/2}.PK samples will be analyzed for all subjects in each cohort prior to dose escalation. These data will be used as adjunct information for a safety review, which will include a review of adverse events, changes in vital signs, physical examination and clinical laboratory test results.

If the starting dose (50 mg/day) for Cohort 1 (Part A) results in a total benzamide (LB-101 and LB-102) geometric mean C_{max} greater than 175 ng/mL or a geometric mean of total benzamide exposure (AUC_{inf}) greater than 3,270 ng/mL*h, the dose for Cohort 2 will be adjusted downward, to the nearest 10 mg, by the equations below (equations are based on the observed PK and assume dose linearity). The equation producing the lower dose will be selected. If the terminal phase PK is not captured adequately by the last time point collection, time will be extended to capture at least 2 time points of the terminal phase. Upon collection of the PK from Cohort 2, the human PK model will incorporate the human PK data and any elements of non-dose-linear PK. Dosing of the 3rd cohort will resume at 100 mg unless there is a clinical concern with safety in Cohort 2. If there is a clinical concern in Cohort 2, the SRC will convene and determine an appropriate dose for Cohort 3. Dose escalation is designed to at least capture the exposure range listed in Table 3 with the intent to exceed a C_{max} of 1,200 ng/mL and or an AUC_{inf} of 16,000 ng/mL*h (Refer to Section 6.8) unless there are clinical findings limiting further escalation. Dose escalation to 200 mg in Cohort 4 and 400 mg in Cohort 5 will be dependent on clinical observations.

 $Dose \ 2 = 50 \ mg * C_{max} \ 35 \ ng/mL \ / \ Observed \ C_{max} \ (ng/mL)$ or $Oose \ 2 = 50 \ mg * AUC_{inf} \ 655 \ ng/mL*h \ / \ Observed \ AUC_{inf} \ (ng/mL*h)$

Table 3: Target C_{max} and AUC_{inf} for Total Benzaminde Plasma Concentration Resulting from Dosing LB-102

Dose (mg)	C _{max} (ng/ml)	AUC _{inf} (ng/ml*h)
10	35	330
50	173	1648
100	346	3297
200	692	6593
400	1384	13186

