7.2.4 Treatment Evaluation (Visit 3, Days 2-7)

The following procedures will be performed on Days 2-7:

- Dosing at 8 AM and 8 PM (±1 hour) intervals on Days 2-6 (AM only on Day 7).
- Physical exam (prior to first dose on Days 2 and 4 only).
- Vital signs (prior to first dose and 2 hours (± 30 min) post first dose on All Days).
- Plasma sample for PK analysis (Refer to Table 2).
- 12-lead ECG (prior to first dose on All Days).

- Blood and urine samples for clinical laboratory tests (hematology, clinical chemistry, urinalysis, and prolactin) prior to first dose on Day 4 only.
- C-SSRS (Day 4 only).
- Record concomitant medication use (prior to first dose on All Days).
- Assess and record AEs (prior to first dose on All Days).

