7.2.5 Treatment Evaluation (Visit 3, Day 8)

The following procedures will be performed on Day 8:

- Plasma sample for PK analysis (24 and 32 hours (±15 min) post Day 7 dose).
- Physical examination.
- Vital signs (24 hours (±30 min) post Day 7 dose).
- 12-lead ECG (24 hours (±30 min) post Day 7 dose).
- Collect blood and urine samples for clinical laboratory tests (hematology, clinical chemistry, urinalysis).
- C-SSRS.
- Record concomitant medication use.
- Assess and record AEs.

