8.5.6 OT Prolongation Stopping Criteria

Dosing of an individual subject will cease if any of the following criteria are met:

• An increase in QTcF to > 500 msec for male and female subjects.

OR

• An increase in QTcF of > 60 msec over baseline.

ECG will be measured once in Part A for Cohorts 1-4. ECG will be measured in triplicate in Part A for Cohort 5 and Part B, mean values will be used for Stopping Criteria. A confirmation of an abnormal finding meeting the stopping criteria will be required within 15 minutes of the initial QTcF reading.

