8.5.11 Electrocardiogram

A 12-lead ECG will be performed after the subject has been in supine resting for at least 10 minutes, and at the following times:

Part A: Screening, Check-in, Day at pre-dose and 1, 2, 3, 4, 5, 6, 8, and 24 hours (±30 min) post-dose. ECG will be measured once at each time point for Cohorts 1-4 and in triplicate for Cohort 5.

Part B: Screening, Check-in, Day 1 Pre-dose and 1, 2, 3, 4, 5, 6, and 8 hours (±30 min) post-dose, prior to the first dose on Days 2-7, and Day 8 (24 hours (±30 min) post Day 7 dose). ECG will be measured in triplicate at each time point.

^{*}Serum for pregnancy test and HbA1c assessment are only required at Screening.

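### Part B takes ECGs at 1-8 h only after the first of 13 doses, so no scheduled QTcF reading falls near the steady-state peak

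*Protocol*

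**What the plan says.** The Part B ECG schedule is the same wherever it appears: Synopsis, Table 2 note 3, 5.1, 7.2.3-7.2.5 and 8.5.11. There is a full post-dose set after the first Day 1 dose. Table 2 note 3 ends that set and gives the later times as "post first dose, prior to first dose on Days 2-7, and Day 8 (24 hours (±30 min) post Day 7 dose". For Days 2-7, section 7.2.4 lists "12-lead ECG (prior to first dose on All Days", which is about 12 h after the evening dose. Section 7.2.5 lists the last one as "12-lead ECG (24 hours (±30 min) post Day 7 dose". Section 8.5.11 repeats the pattern: "prior to the first dose on Days 2-7, and Day 8 (24 hours (±30 min) post Day 7 dose". All are triplicate.

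Other measures do cover the peak. Section 7.2.4 has "Vital signs (prior to first dose and 2 hours (± 30 min) post first dose on All Days". For concentrations, 5.1 states "On Day 7 blood samples for PK will be collected pre-dose and at 15, 30, and 45 minutes", continuing through 1, 1.5, 2, 3, 4, 6 and 8 h and later. Section 5.1 also fixes what happens when procedures coincide: "in the following order: ECG, Vital Signs, and then PK blood collection".

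Dosing of a subject stops under 8.5.6 if QTcF exceeds 500 msec or on "An increase in QTcF of > 60 msec over baseline". Section 8.5.5 stops a cohort if two or more subjects meet that rule. The Safety Review Committee (SRC) sets the Cohort 7 and 8 doses from the preceding cohort's safety data through Day 9.

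**The concern.** Concentration is highest some 2-3 h after a dose once accumulation is complete, and that is where a concentration-related QTcF effect would be expected to be largest. The plan looks at that time after dose 1, before any accumulation, and not after doses 2-13.

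Two decisions depend on these ECGs. The stopping rule in 8.5.6 has no scheduled peak-time reading after Day 1. The SRC would choose the next BID dose from first-dose peaks and later troughs, without a reading at the highest exposure the cohort reached. Clean ECGs on Days 2-8 would be weaker reassurance than they appear.

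**Working it through.** **Inputs.** 13 doses at about 12 h intervals (5.1, 6.3). From Appendix 1: mean Tmax 2.083-3.167 h, mean terminal half-life 12.311-14.656 h, and a repeat-dose model figure of 40% accumulation on Cmax.

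**Count.** Doses: 2 x 6 + 1 = 13, as stated. Scheduled ECG times within 1-8 h of a dose: 7 after dose 1, 0 after doses 2-13. This step needs no model.

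**Accumulation.** The Appendix 1 wording is ambiguous. Read as a steady-state to first-dose Cmax ratio, it gives R = 1.4. The terminal half-lives, put into 1/(1 - 2^(-12/t½)), give 2.04 (12.311 h) to 2.31 (14.656 h). R = 1.4 would need an effective half-life of 12 ln2 / (-ln(1 - 1/1.4)) = 6.64 h. A multiphasic decline could reconcile the two, so this is not an error, but both readings must be carried.

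**Reading 1, R = 1.4.**
- Simple superposition. Day 1 share of the steady-state peak: 1/1.4 = 71%. Pre-dose share: 0.4 x 2^(Tmax/t½)/1.4, from 0.4 x 2^(2.083/14.656)/1.4 = 0.315 to 0.4 x 2^(3.167/12.311)/1.4 = 0.341. Day 8: multiply by 2^(-12/t½), giving 0.163-0.188.
- One-compartment oral model with half-life 6.64 h, ka solved from ln(ka/ke)/(ka - ke) = Tmax, and 13 doses superposed: Cmax ratio 1.44-1.48; Day 1 67-69%, pre-dose 34-44%, Day 8 11-13%.

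**Reading 2, stated terminal half-lives.** In the same one-compartment model, each cohort's own Tmax and half-life give a Cmax ratio of 2.12-2.39.

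| Share of steady-state peak seen by | Reading 1 | Reading 2 |
|---|---|---|
| Day 1 ECGs, at best | 67-71% | 42-47% |
| Pre-dose ECGs, Days 2-7 | 32-44% | 43-65% |
| Day 8 ECG | 11-19% | 31-37% |

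**Indirect cover from Part A.** Peaks as single-dose equivalents (dose x R):
- 50 mg BID: 50 x 1.4 = 70 mg, or about 106-120 mg on reading 2. Both lie below the 150 mg (triplicate ECG) and 200 mg (single ECG) tested.
- 100 mg BID: 100 x 1.4 = 140 mg, or about 210-240 mg on reading 2. The second is above anything tested.

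**Day 4 as an early look.** Six doses precede Day 4, so its first dose is number 7 and 6 remain. In the model runs, the concentration 2-3 h after that dose is at least about 94% of the Day 7 peak.

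**The case against.** The schedule is consistent throughout, so this is a design choice and not a contradiction. Part A took ECGs across the peak up to 200 mg, and nothing bars the SRC from using them. The only fixed Part B dose, 50 mg BID, stays inside that range on either reading. The SRC sets later doses, and dosing or escalation can stop for any event judged an unacceptable risk. All of this stands. It limits the gap, but it supplies no peak ECG under repeat dosing.

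A reader might go further and infer from Cohort 4 that LB-102 has a brief QTcF effect at peak that trough ECGs are bound to miss. The documents do not support that. Appendix 1 reports one subject at 200 mg with QTcF above 450 msec at 2 h, resolved by 3 h, in a cohort with single ECGs. The maximum rise of 43 msec met no stopping threshold and has no stated time. Resolution of that AE does not mean a return to baseline. With the 200 mg mean Tmax of 2.083 h, the modelled 3 h concentration is still about 96-98% of peak, so single-ECG variability is also a candidate. The 150 mg cohort, in triplicate, lists no QTcF AE. The event shows that a reading near peak can matter, and no more.

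Equally, it would be too much to say that Part B peaks will exceed Part A. At 100 mg BID that is true on one reading of accumulation and false on the other, and the Cohort 7 and 8 doses are not set.

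**Conclusion.** The gap is real and should be closed. After dose 1, no scheduled ECG in Part B lies near a peak, so the stopping rule and the escalation review have no direct QTcF reading at the highest exposure reached. That conclusion rests on the schedule and Tmax alone.

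Its size is conditional. The shares assume linear PK and either a Cmax ratio of about 1.4 or one-compartment accumulation from the terminal half-lives, with cohort mean values standing in for individuals. On both, the best-placed ECG sees no more than about 71% of the steady-state peak. For 50 mg BID the loss is a missing direct reading under repeat dosing, at an exposure Part A already covered. For 100 mg BID, whether Part A gives that cover depends on which accumulation figure is right.

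**What to change.** For Cohorts 6-8, amend Table 2 note 3 and the matching text in the Synopsis, 5.1, 7.2.4 and 8.5.11:

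1. Take triplicate ECGs at 2, 3 and 4 h after the Day 7 dose (optionally also 1 and 6 h), just before the PK draws already due then, and have the SRC review them before setting the next dose. Cost: 3 x 8 subjects x 3 cohorts = 72 extra triplicate sets, or 5 x 8 x 3 = 120 with the optional times. Subjects are already confined, and no visit or blood draw is added.
2. Day 7 is the last dose, so those readings cannot stop anyone's dosing. Also take a triplicate ECG about 2-3 h after the first Day 4 dose, when 6 doses remain and 8.5.6 can still act. At 2 h it falls alongside vital signs already scheduled.
   - Moving the Day 4 pre-dose ECG to this time adds no set, but loses that trough ECG and its matched PK sample, because no PK is drawn at that time on Days 2-6.
   - Adding the reading instead keeps the trough and costs 1 x 8 x 3 = 24 sets. This is the cleaner choice.

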2. LIST OF ABBREVIATIONS AND DEFINITIONS OF TERMS

Abbreviation	Definition
AE	Adverse Event
API	Active Pharmaceutical Ingredient
ASI	Application Setup Instructions
AVB	Atrioventricular Block
BID	Twice a Day
BMI	Body Mass Index
CL	Corpora Lutea
CNS	Central Nervous System
COV	Close-Out Visit
CRF	Case Report Form
CRO	Contract Research Organization
CSR	Clinical Study Report
C-SSRS	Columbia-Suicide Severity Rating Scale
D ₂	Dopamine (D ₂) Receptors
DM	Data Management
DMP	Data Management Plan
DVP	Data Validation Plan
ECG	Electrocardiogram
EDC	Electronic Data Capture
EPS	Extrapyramidal Side Effects
eCRF	electronic Case Report Form
eTMF	electronic Trial Master File
FDA	US Food and Drug Administration
FGA	First Generation Antipsychotics
FSH	Follicle-Stimulating Hormone
GCP	Good Clinical Practice
GLP	Good Laboratory Practice
HbA1c	Hemoglobin A1c
HBsAg	Hepatitis B Surface Antigen

Abbreviation	Definition
HCV	Hepatitis C Virus
HED	Human Equivalent Doses
HIPAA	Health Insurance Portability and Accounting Act
HIV	Human Immunodeficiency Virus
ICH	International Conference on Harmonisation
IMP	Investigational Medicinal Product
IRB	Institutional Review Board
LBBB	Left Bundle Branch Block
LCRA	Lead Clinical Research Associate
MAD	Multiple Ascending Doses
MedDRA	Medical Dictionary for Regulatory Activities
NOAEL	No-Observed-Adverse-Effect-Level
PI	Principal Investigator
PK	Pharmacokinetic
PO	Oral/by mouth
QD	Once Daily
RBBB	Right Bundle Branch Block
SAD	Single Ascending Dose
SAE	Serious Adverse Event
SAP	Statistical Analysis Plan
SGA	Second Generation Antipsychotics
SIV	Site Initiation Visit
SRC	Safety Review Committee
SOC	System Organ Class
SQV	Site Qualification Visit

3. INTRODUCTION

3.1 Background and Rationale

Schizophrenia is a chronic and debilitating mental illness that affects approximately one percent of the population. Schizophrenia manifests in delusional behavior, dysfunctional thinking, agitated body movement, social withdrawal, and depression. Schizophrenia patients suffer a profoundly reduced quality of life and are ten times more likely to commit suicide than the general population (Harris and Barraclough, 1997). Half of suicides among patients with schizophrenia occur within the first two years of disease onset (Tandon and Jibson, 2003), pointing to the urgency for behavioral and pharmaceutical intervention.

There are at least 22 drugs (both first- and second-generation antipsychotics) approved by the FDA indicated for the treatment of schizophrenia (HHS, 2012; FDA, 2015). Despite a seeming surfeit of available drugs to treat schizophrenia, adequate treatment of schizophrenia remains a challenge. Non-adherence and discontinuation of treatment is a major issue. A review of randomized, double-blind clinical trials involving schizophrenia or related disorders found that 53% of patients stopped their treatment at an early stage and the most prevalent reasons were poor response or psychiatric symptom worsening (Liu-Seifert et al., 2005). Discontinuation of treatment significantly increases the chance of relapse with an estimated relapse rates of approximately 80% and 95% after discontinuing treatment for 12 and 24 months, respectively (Emsley et al., 2013).

Schizophrenia is a lifelong disease for the majority of patients. The course of schizophrenia is highly variable with periods of psychosis and stabilization of varying duration and intensity. Sustained remission of both positive and negative symptoms occurs in a minority of patients even with prolonged antipsychotic therapy. It is common for patients to have little or no response to an individual antipsychotic, necessitating the many therapeutic options currently available. Many patients, even when stable, suffer disability due to the cognitive and social deficits that occur despite adequate antipsychotic therapy. Compliance with long-term medication is a significant problem due to dissatisfaction with antipsychotic side effects, or self-discontinuation of medication as a result of feeling better and no longer perceiving the need for continuous medication. Both of these issues contribute to relapse among schizophrenia patients.

The standard pharmacologic mechanism of action for antipsychotic drugs is antagonism of dopamine (D₂) receptors in the limbic system of the brain (Meltzer and Stahl, 1976, Joyce and Meador-Woodruff, 1997, Wulff et al., 2015). This has remained largely unchanged since antipsychotics began use clinically in the 1950s. Second Generation Antipsychotics (SGAs), also known as Atypical Antipsychotics, are preferred by patients and clinicians and are used in the majority of patients. Older antipsychotics developed between 1950 and 1980 are referred to as first Generation Antipsychotics (FGAs) and are used primarily when patients have failed numerous SGAs. The primary advantage of SGAs is a lower incidence of Extrapyramidal Side Effects (EPS) that resemble the types of movement disorders that occur in Parkinson's disease. Patients who experience EPS from a specific antipsychotic will often ask for a different drug or discontinue on their own. While SGAs were an important advance, these drugs are not free of the common side effects of many CNS drugs that arise from varying degrees of antagonism of dopamine, histamine, serotonin, muscarinic, hERG, and alpha receptors. Further, these drugs distribute widely throughout the CNS due to their ability to easily cross the blood brain barrier by passive diffusion

allowing off-target effects to occur. SGA side effects as a result of off-target receptor engagement include weight gain, elevations in lipids and blood sugar, sedation, dry mouth, constipation, dizziness and falls due to low blood pressure, QT interval prolongation, cognitive impairment, and prolactin elevation. Until a disease modifying therapy is developed for schizophrenia, the ideal antipsychotic would be a drug that has selectivity for the limbic system and minimal to no engagement of receptors that cause side effects.

LB-102 was designed to be an improved version of the benzamide antipsychotic amisulpride having increased permeability across the blood-brain-barrier, potentially decreasing the plasma concentrations needed to achieve efficacy thereby decreasing the magnitude and frequency of adverse events typically observed in patients treated with amisulpride.

Amisulpride, originally developed in France in the 1980s (Thominet et al., 1983), is approved in more than 50 countries worldwide for the treatment of schizophrenia and in certain countries for the treatment of dysthymia (IMS, 2015). Amisulpride elicits its activity in part by selectively blocking the human dopaminergic D_2 (K_i 2.8 nM) and D_3 (K_i 3.2 nM) receptor with negligible affinity for the D_1 , D_4 , and D_5 receptor subtypes ($K_i > 1,000$ nM) and in part by its activity against the 5-HT7 receptor (11.5 nM K_i). While amisulpride is a clinically effective drug, it demonstrates poor distribution to the brain. A 2014 study (Dos Santos Pereira et al., 2014), revealed that passive diffusion of amisulpride across a PAMPA membrane was the lowest of 30 psychiatric drugs tested (Figure 1).

